1.1 SUMMARY

Title:	Effect of Structured Progressive Task-Oriented Circuit Class Training With Motor Imagery on Gait in Stroke
Clinical registration no:	NCT03436810
Document Date:	January 18, 2017
Study Description:	Structured Progressive Circuit Class Training (SPCCT) has developed on the basis of task-oriented therapy, provides the enriched benefits on the patients' motivation and motor function. Training with the Motor Imagery (MI) alone can improve gait performance in patients with stroke, but the better effect may observe if combined with the SPCCT. Thus, the aim of this study was to investigate the effect of MI with SPCCT on gait in patients with stroke. The study involved forty patients with stroke from 3 hospitals in Yangon, Myanmar. All participants received the 90 min intervention in a session. The experimental group received MI with SPCCT and control group received HE with SPCCT intervention 3 times a week for 4 weeks. The assessments were taken at the baseline, 2 week and 4 weeks after intervention. The outcomes measures involved spatio-temporal variables, walking endurance, dynamic balance, mobility function and muscle strength.
Objectives:	
General Objective: To investigate the effect of MI with SPCCT on gait performance in patients with stroke
 
Specific Objectives: To investigate the spatio-temporal and functional gait variables in patients with stroke after receiving MI with SPCCT
 
To investigate the spatio-temporal and functional gait variables in patients with stroke after receiving HE with SPCCT
 
To compare the effect of MI with SPCCT and HE with SPCCT on the spatio-temporal and functional gait variables in patients with stroke.

Outcome measures:	Spatio-temporal variables, walking endurance, dynamic balance, mobility function, muscle strength
Study Population:	Forty patients with stroke, age for experimental group was 49.90 ± 11.59 years and control group was 55.55 ± 10.74 years, 15 males and 5 females for experimental group and 11 males and 9 females for control group, Mean height for experimental group was 163.89 ± 6.55 centimeters and control group was 162.03 ± 13.04 centimeters. Mean weight for experimental group was 63.65 ± 6.63 kilograms and control group was 63.35 ± 13.04 kilograms

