1.5 PROCEDURE

All participants will be explained about details of the study and the interventions. After that, they will be asked to sign on the written consent approving by the committee of the institution prior to participate in study. All participants will be randomly allocated the participants into the experimental (SPCCT with MI) or the control (SPCCT with health education) groups. All participants will be screened following the criteria and will be collected the demographic data.

Both groups will receive the same program of SPCCT by physiotherapist who have 5 years experienced in neurological condition. Prior to training, tasks will be demonstrated using clear instructions. Seven lower extremity mobility tasks will be used in the SPCCT program. The tasks were selected from the study of Dean et al and adapted to be appropriate for improving gait function in patients with stroke. The trained tasks for the MI will be similar to the tasks in SPCCT to getting the transfer effects of training. The experimental group will receive MI training, whereas, the control group will receive health education which both will be provided by the researcher. Both groups will be matched for duration and frequency of the therapy sessions.

All outcome measures will be assessed by the therapist who have been trained the outcome measures of the study. As the primary outcome measurements, spatio-temporal variables will be measured by using two dimensional motion analysis method. The protocol of this method was proved to be valid and reliability from previous pilot study. For functional gait variables, six-minute walk test will be assessed for determining walking endurance, step test will be assessed for dynamic balance, and Timed Up and Go (TUG) test will be assessed for mobility function.

As the secondary outcome measure, the strength of hip flexor, hip extensor, knee flexor, knee extensor, ankle dorsiflexor, and ankle plantarflexor muscles will be assessed by using hand-held dynamometer. Muscle spasticity will be assessed by using the Modified Ashworth Scale (MAS). The outcome measures will be assessed at the baseline, after 2 weeks and 4 weeks intervention. For the safety, the therapist will measure blood pressure, pulse rate and fatigue level in the assessments, just before the training, and rest period during the training program.

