Statistical analysis plan

Title: Effect of Structured Progressive Task-Oriented Circuit Class Training With Motor Imagery on Gait in Stroke

Clinical registration no: NCT03436810

Documentt date: January 18, 2017

Statistical analysis plan:

All data will be tested by the SPSS version 18.0 with a significant value of $p < 0.05$ for all comparisons. The demographic data of the participants will be presented with mean, standard deviation, and range for the continuous variables. Frequency and percentage will be presented for the categorical variables.

Normality will be tested by the Kolmogorov Smirnov Goodness of Fit test, for normally distributed variables, a two-way mixed repeated measure ANOVA will be tested to investigate the effect of group and time on the outcome measures. In addition, the interaction effect of the group by time will be detected. For the non-normally distributed variables, the Mann-Whitney U test (between-group) and the Friedman ANOVA test in conjunction with the Wilcoxon Signed-Rank test (within-group) will be used.

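### The SAP names no term, visit or contrast as the answer to motor imagery versus health education, and it does not use the measured baseline as a covariate

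*SAP*

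**What the plan says.** The comparative objective in Protocol section 1.1 is "To compare the effect of MI with SPCCT and HE with SPCCT on the spatio-temporal and functional gait variables in patients with stroke". Section 1.5 sets three assessments: "The outcome measures will be assessed at the baseline, after 2 weeks and 4 weeks intervention".

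For normally distributed outcomes the SAP states that "a two-way mixed repeated measure ANOVA will be tested to investigate the effect of group and time on the outcome measures". The next sentence reads "In addition, the interaction effect of the group by time will be detected". For the remaining outcomes, "the Mann-Whitney U test (between-group) and the Friedman ANOVA test in conjunction with the Wilcoxon Signed-Rank test (within-group) will be used". One threshold applies throughout: "with a significant value of $p < 0.05$ for all comparisons".

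Neither document names a primary visit, designates one ANOVA term as the treatment test, or plans a between-group contrast after the interaction. No analysis includes a covariate. The Mann-Whitney test is the only between-group test on the non-normal route, and it has no stated visit and no stated scale (value or change from baseline). The SAP does not spell out that baseline is a level of the time factor. With three assessments and no other role for baseline, that is a fair inference.

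**The concern.** The two ANOVA terms that involve group answer different questions, and the plan does not say which one counts.

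- **Group main effect.** It has 1 df, so it gives an MI-HE difference with an interval, but averaged over visits. If one of those visits is baseline, where randomisation makes the expected difference zero, the average is diluted.
- **Group-by-time interaction.** It tests whether the arms change differently, which is the relevant question. As a 2-df F test it does not say which arm did better, at which visit or by how much, and no follow-up contrast is planned.

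The non-normal route has a similar gap. Mann-Whitney could be applied at week 2 or week 4, to values or to changes, and no adjustment for baseline is stated.

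The trial could therefore finish without a pre-specified estimate for its comparative objective, and the choice of result could be made after the data are seen.

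**Working it through.** **Inputs from the documents.** 20 participants per arm (Protocol 1.1: 15 + 5 and 11 + 9); visits at baseline, week 2 and week 4 (Protocol 1.5); threshold 0.05 (SAP).

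**Assumptions.** The documents give no outcome SD, between-visit correlation r or target difference. The figures below use SD 1, two-sided tests, independent participants, r from 0.5 to 0.9, and compound-symmetric or AR(1) correlation. Simulations used 20,000 trials per scenario unless stated. The plan states no figure of its own on this point, so there is none to reproduce.

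**1. What the group main effect estimates.** Let d2 and d4 be the MI-HE differences at weeks 2 and 4. If baseline is a level of time with expected difference zero, the main effect estimates (0 + d2 + d4)/3 = d4(1 + f)/3, where f = d2/d4. This is one third to two thirds of d4 when d2 lies between zero and d4. For d4 = 0.8 SD:

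- linear course, f = 0.5: 0.8 × 1.5/3 = 0.40 SD
- early course, f = 1: 0.8 × 2/3 = 0.53 SD
- late course, f = 0: 0.8 × 1/3 = 0.27 SD

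**2. Null error if either term could be claimed.** For two independent tests, 1 − 0.95² = 9.75%. Simulation gives 9.4 to 10.7% across both correlation structures.

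**3. Null error on the Mann-Whitney route.** If week 2 or week 4 could be claimed, the simulated rate is about 6.5 to 9%. If value or change could also be chosen, it is about 14 to 16%. The lowest figures (6.5% and 13.9%) occur under AR(1) with r = 0.9, from 8,000 trials per scenario.

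**4. Precision of the week-4 contrast, compound symmetry.** The change-score contrast has SE = √(2/20) × √(2(1 − r)). With baseline as covariate, SE = √((2/20)(1 − r²)(1 + 1/36)), where 36 = 40 − 4.

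| r | SE, change | SE, covariate (formula) | SE, covariate (simulated mean) | Reduction (simulated) |
|---|---|---|---|---|
| 0.5 | 0.316 | 0.278 | 0.276 | 1 − 0.276/0.316 = 12.7% |
| 0.7 | 0.245 | 0.229 | 0.227 | 1 − 0.227/0.245 = 7.3% |
| 0.8 | 0.200 | 0.192 | 0.191 | 1 − 0.191/0.200 = 4.5% |
| 0.9 | 0.141 | 0.140 | 0.139 | 1 − 0.139/0.141 = 1.4% |

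**5. Choice of rank method.** Power (%) for a 0.8 SD week-4 effect at r = 0.5/0.7/0.8:

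| Correlation | Mann-Whitney, value | Mann-Whitney, change | Rank ANCOVA |
|---|---|---|---|
| Compound symmetry | 66/66/67 | 67/87/97 | 77/89/96 |
| AR(1) | 67/66/66 | 50/66/81 | 68/76/85 |

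Rank ANCOVA keeps its level (null size 4.8 to 5.1%). It avoids the loss that the change score suffers when baseline predicts week 4 weakly.

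**The case against.** The strongest reply is that a valid treatment test is already in the plan. With baseline as a level of time, the interaction compares change from baseline between arms, so baseline is not ignored. That stands. What is missing is its designation, a contrast with an interval, and the more efficient use of baseline. The gain from a covariate is modest and nearly vanishes at r = 0.9.

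A second reply is that a single-visit contrast can lose power, and this also stands. If the effect is 0.8 SD at week 2 and fades to 0.4 SD at week 4, interaction power is 0.60/0.82/0.95 against 0.29/0.40/0.53 for week-4 ANCOVA (compound symmetry, r = 0.5/0.7/0.8). Under AR(1) with r of 0.7 to 0.8, the interaction also leads by 3 to 6 points for a 0.8 SD effect that comes early or late. Part of that lead reflects its uncorrected null size of 5.3 to 5.8%.

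Three stronger readings are tempting, and the documents do not support them:

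- **The group main effect is the planned treatment test.** The SAP mentions it before the interaction but does not say that it decides.
- **The plan has a 10% or 16% type I error.** Those rates need a rule that any significant term, visit or scale may be claimed. A 0.05 threshold for every comparison is not such a rule.
- **ANCOVA is generally more powerful than the interaction.** The fading course above is a counterexample.

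The calculations also treat participants as independent, although Protocol 1.6 has them train in pairs.

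**Conclusion.** The point holds as a gap in specification that should be closed. It does not show that the analysis is invalid. That no term, visit, contrast or Mann-Whitney scale is designated, and that no baseline covariate is planned, can be read directly from the text and needs no assumption.

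The sizes are conditional. The dilution to (d2 + d4)/3 requires baseline to be a level of time and a zero expected baseline difference, and it matters only if the main effect is read as the treatment effect. The error rates show what an open choice could cost: about 10% for the two ANOVA terms, 6.5 to 9% for the Mann-Whitney visit, and 14 to 16% for visit and scale together. The reduction in SE from a baseline covariate, about 13% at r = 0.5, 7% at 0.7, 4 to 5% at 0.8 and 1 to 2% at 0.9, assumes compound symmetry.

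**What to change.** - **Primary comparison.** Name one baseline-adjusted MI-HE contrast at one visit, for example week 4, the end of the programme, and report it with its 95% CI. Use either a week-4 ANCOVA or a model of week-2 and week-4 values with group, visit, group-by-visit, baseline and baseline-by-visit. With complete data and unstructured covariance the two give the same week-4 estimate. Include the randomisation stratum, which Protocol 1.2 mentions without saying what defines it.
- **Supporting results.** Keep the group-by-time interaction as a supporting test and report the week-2 contrast as secondary, so that an early effect that fades is not missed. Do not interpret a group main effect that includes baseline.
- **Non-normal outcomes.** Use rank ANCOVA on baseline at the same visit.
- **Timing.** Fix the choice before outcome data are examined. Protocol 1.1 already describes the forty participants in the past tense, and the documents do not show whether outcomes had been looked at. If they had, label the choice post hoc.

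The cost is SAP wording and slightly different code, since all three assessments are already planned. The drawback is the lower sensitivity of one visit to an effect that peaks early, which the secondary contrast and the retained interaction are there to cover.

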1.3 SELECTION CRITERIA

Inclusion criteria

1. First stroke diagnosed by neurologists and has paresis on the unilateral side of the body
2. Age between 18 and 75 years
3. Poststroke duration between 3–12 months confirmed by CT report.
4. Patients with middle cerebral artery (MCA) involvement
5. Ability to walk at least 10 meters with or without using assistance (walking aid and/or orthosis).
6. Functional Ambulation Category (FAC) ≥ 3 from the total of 5 score
7. Good cognition assessing by the Mini Mental State Examination (MMSE) ≥ 24 from the total of 30 score
8. National Institutes of Health Stroke Scale (NIHSS) < 14 from the total of 42 score
9. Proper MI ability assessing by the Kinesthetic and Visual Imagery Questionnaire (KVIQ–10) ≥ 3 from the total of 5 score

Exclusion criteria

1. Unstable cardiopulmonary problems (resting heart rate > 120 bpm, resting systolic blood pressure > 180 mmHg and resting diastolic blood pressure > 100 mmHg)
2. Other neurological conditions such as Parkinson's disease, Alzheimer's disease, or epilepsy
3. Orthopedic and rheumatologic disorders with weight bearing pain
4. Unable to communicate or unable to follow commands
5. Serious cardiac conditions such as hospitalization for heart disease within 3 months, active angina, serious cardiac arrhythmias, hypertrophic cardiomyopathy, severe aortic stenosis
6. Patients with unilateral spatial neglect
7. Patients with ataxic movement
8. Patients under medications with muscle relaxing effect

Termination Criteria

1. Borg scale for Rating Perceived Exertion (RPE) > 13 from the total of 20 score
2. Drop in systolic blood pressure 10 mmHg (persistently below baseline), despite an increase in workload, when accompanied by any other evidence of ischemia
3. Central nervous system symptoms such as dizziness, or near syncope
4. Signs of poor perfusion such as cyanosis or pallor
5. Severe adverse event, this means falls or incidents leading to injury requiring hospital or general practitioner visit
6. Another episode of stroke

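### For normally distributed outcomes the planned ANOVA drops anyone without all three visits, and the SAP sets no missing-visit rule and no sphericity correction for the group-by-time test

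*SAP*

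**What the plan says.** The SAP is two paragraphs long. For outcomes judged normal, "a two-way mixed repeated measure ANOVA will be tested to investigate the effect of group and time on the outcome measures", followed by "In addition, the interaction effect of the group by time will be detected". The level is set "with a significant value of $p < 0.05$ for all comparisons", and the software is SPSS 18.0 with no procedure named. For outcomes judged non-normal, the arms are compared by Mann-Whitney, and change within each arm is examined by Friedman and Wilcoxon tests. The SAP does not define the analysis set, the handling of a missing visit, a check of sphericity, or which line of the repeated-measures output gives the p-value.

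There are three measurements per participant: "The outcome measures will be assessed at the baseline, after 2 weeks and 4 weeks intervention" (Protocol 1.5). The Protocol Summary describes 40 participants, 20 per arm (15 + 5 and 11 + 9).

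Protocol 1.3 lists six termination criteria. They range from a reading that may pass within a session, "Borg scale for Rating Perceived Exertion (RPE) > 13 from the total of 20 score", to lasting events such as a new stroke or "Severe adverse event, this means falls or incidents leading to injury requiring hospital or general practitioner visit". The list does not say whether each item ends the session, the training or the outcome assessments.

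**The concern.** The group-by-time interaction is the SAP's test of whether the arms change differently, so it carries the treatment comparison for normally distributed outcomes. Two features of the method bear on it.

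First, a classical repeated-measures ANOVA needs a complete row for each participant. With no rule for filling gaps, a participant who misses week 2 or week 4 is removed altogether, including the visits that were recorded. Falls, near syncope and recurrent stroke are plausibly related to walking ability. If such events lead to missed visits, the loss need not be random, and with 20 per arm there is little to spare. What is compared is then the completers, not everyone randomised.

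Second, the uncorrected interaction F test assumes that the differences between every pair of visits have equal variance. That is doubtful if the two post-baseline visits, two weeks apart and both under training, resemble each other more than either resembles baseline. When the assumption fails, the uncorrected test rejects too often. A Greenhouse-Geisser line or a multivariate line would give a different p-value, and the SAP does not say in advance which one counts.

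**Working it through.** **Inputs.** From the documents: 3 visits, 20 per arm, level 0.05. Assumed, because the documents give none: correlations between visits, equal variances across visits, and all dropout rates. The sample size of 40 has no stated derivation, so there is no figure of the plan to reproduce except the 5% level.

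**1. Type I error of the uncorrected interaction test.** Degrees of freedom are (2−1)(3−1) = 2 and (40−2)(3−1) = 76; the 5% critical value of F(2, 76) is 3.12.

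- Under sphericity (epsilon = 1), simulation gives 5.0%, so the stated level is reproduced.
- With three visits the lowest possible epsilon is 1/(3−1) = 0.5. All within-person variation then lies in one contrast and the statistic follows F(1, 38). P[F(1, 38) > 3.12] = 8.6%. This is the ceiling.
- In between, let λ1 and λ2 be the variances of the two orthonormal visit contrasts. Epsilon = (λ1 + λ2)² / [2(λ1² + λ2²)]. With both baseline correlations equal to r and week 2–week 4 correlation s, λ1 = 1 − s and λ2 = (3 − 4r + s)/3. For r = 0.65 and s = 0.95: λ1 = 0.05, λ2 = 0.45, epsilon = 0.25/0.41 = 0.61.

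| Assumed correlations (baseline–wk 2, baseline–wk 4, wk 2–wk 4) | Epsilon | Uncorrected | Greenhouse-Geisser |
|---|---|---|---|
| 0.70, 0.70, 0.70 | 1.00 | 5.0% | 4.7% |
| 0.90, 0.90, 0.95 | 0.86 | 5.6% | 4.7% |
| 0.80, 0.64, 0.80 (autoregressive) | 0.85 | 5.7% | 4.8% |
| 0.70, 0.70, 0.90 | 0.75 | 6.3% | 4.9% |
| 0.80, 0.80, 0.95 | 0.69 | 6.7% | 4.9% |
| 0.60, 0.50, 0.90 | 0.66 | 7.0% | 5.0% |
| 0.90, 0.80, 0.95 | 0.64 | 7.2% | 5.0% |
| 0.65, 0.65, 0.95 | 0.61 | 7.4% | 5.0% |

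Simulated, complete normal data, one million draws per row. Separate runs differ by about 0.1 percentage point.

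**2. Participants left after deletion.** If a proportion q is missing at each of the two follow-up visits, 40(1−q)² remain when the gaps are independent and 40(1−q) when the same people miss both. For q = 5%, 10% and 15% that is 36.1, 32.4 and 28.9, or 38, 36 and 34.

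**3. Precision.** The standardised difference detectable with 80% power at one visit is about (1.96 + 0.84)√(2/n): 0.89 SD at n = 20 per arm, 0.93 at 18 and 0.99 at 16. The noncentral t gives 0.91, 0.96 and 1.02.

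**4. Bias.** Simulated with no true effect, correlations 0.8/0.7/0.85, and the participants with the worst week-2 change missing at week 4. The completers' comparison of change to week 4 gave:

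| Loss, experimental vs control | Bias (SD) | Rejection rate |
|---|---|---|
| 20% vs 20% | about 0 | 7.2% |
| 10% vs 0% | 0.10 | 7.0% |
| 20% vs 5% | 0.13 | 9.1% |
| 20% vs 0% | 0.19 | 11.8% |

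A likelihood-based estimate using all recorded visits had bias of at most 0.004 SD in the same settings. A milder assumed mechanism, with dropout depending on the week-2 value in one arm only, gave completer bias of just 0.02–0.03 SD.

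**5. The remedy needs its own check.** With complete data, the unstructured mixed-model test of the interaction is Hotelling's T². Referred to chi-square with 2 degrees of freedom (critical value 5.99), it rejects with probability P[F(2, 37) > 5.99 × 37/76] = 6.7%. Small-sample degrees of freedom are needed to bring this back to about 5%.

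**The case against.** A reader might infer that terminated patients leave the comparison. The protocol does not say so. Several items on the list can be read as stopping a session only, nothing says that assessment ends, and no number of terminations or dropouts is given. Deletion follows only if a visit is missed.

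A reader might also infer that the 5% error rate is not kept. That too goes beyond the text. The level holds under sphericity, and the SAP does not say that the uncorrected line will be used; repeated-measures output commonly offers corrected and multivariate tests as well. The defect is that the choice is left open.

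Three further limits stand:

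- The problem does not cover the whole plan. Mann-Whitney needs neither all three visits nor sphericity. Friedman does need complete rows, but it is used within arms and does not touch the randomised comparison. The main effect of group does not depend on sphericity, although it loses the same incomplete participants.
- The larger error rates need a week 2–week 4 correlation well above the baseline correlations. With 0.90, 0.90 and 0.95 the rate is only 5.6%.
- The precision loss in step 3 is not wholly the price of choosing ANOVA. A mixed model cannot restore unseen week-4 values; it recovers part of the information through the correlation with earlier visits.

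What remains is that the named method deletes incomplete participants, and nothing in the SAP prevents this or fixes which interaction p-value counts.

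**Conclusion.** The point holds in a conditional form and should be addressed. For normally distributed outcomes, the SAP as written analyses only participants with three complete visits. If the uncorrected interaction test is used and sphericity fails, its type I error is about 5.6% to 7.4% under the assumed patterns and cannot exceed about 8.6% with three visits and 20 per arm. That inflation is moderate.

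Bias from deletion ranges from negligible to 0.19 SD in the scenarios tried. It is material only when loss is related to outcome and differs between arms, and the documents give no dropout figure from which to choose among those scenarios. They support neither a claim that terminated participants are in fact excluded nor a claim that the error rate is in fact exceeded.

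**What to change.** - Replace the ANOVA with a linear mixed model for repeated measures in all randomised participants, analysed as allocated. Include visit and group-by-visit terms, an unstructured covariance over the three visits, and small-sample degrees of freedom (Satterthwaite, or Kenward-Roger where the software offers it). Report the week-4 group difference in change from baseline with its confidence interval.
- If the ANOVA is kept as a supporting analysis, name the Greenhouse-Geisser p-value in advance for the time and group-by-time tests.
- State that participants who stop training are still assessed at weeks 2 and 4 where they can attend.
- Ask the sponsor to clarify which termination items in Protocol 1.3 end a session and which end participation. The clinical rule is for the sponsor.

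The cost is a few sentences in the SAP and protocol, a standard mixed-model procedure, slightly more analysis work, and a few extra assessments in participants who stopped training. The Protocol Summary is written in the past tense; if follow-up is already over, the modelling changes can still be made, but the assessment instruction cannot.

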Description of Sites/Facilities Enrolling Participants:	National Rehabilitation Hospital (NRH), the departments of the Physical Medicine and Rehabilitation in North Okkalapa General Hospital (NOGH) and East Yangon General Hospital (EYGH), Yangon, Myanmar
Description of Study Intervention:	The experimental group received MI with SPCCT and control group received HE with SPCCT intervention 3 times a week for 4 weeks.
Participant Duration:	4 weeks

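### A normality pre-test of unstated form picks the analysis for each outcome, and neither branch fixes one baseline-adjusted comparison of motor imagery with health education

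*SAP*

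**What the plan says.** The SAP is two paragraphs long and is the only analysis text in either document. It starts with a gate: "Normality will be tested by the Kolmogorov Smirnov Goodness of Fit test". Variables that pass go to a two-way mixed repeated-measures ANOVA with group and time. The interaction is then mentioned: "In addition, the interaction effect of the group by time will be detected". Variables that fail go to the other branch, where "the Mann-Whitney U test (between-group) and the Friedman ANOVA test in conjunction with the Wilcoxon Signed-Rank test (within-group) will be used".

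The Protocol (1.5 Procedure) fixes three visits: "The outcome measures will be assessed at the baseline, after 2 weeks and 4 weeks intervention". The third specific objective (1.1 Summary) is the between-arm one: "To compare the effect of MI with SPCCT and HE with SPCCT on the spatio-temporal and functional gait variables in patients with stroke". No Protocol section adds analysis detail that would fill the gaps in the SAP.

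**The concern.** Four things are left open.

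- **KS version:** standard, or with the Lilliefors correction for estimated mean and SD.
- **What is tested:** arms pooled or separate, which visit, raw values or residuals.
- **Which ANOVA effect decides MI versus HE:** the group main effect averages in the baseline visit. The interaction asks whether the arms differ in any pattern over three visits. Neither is named as decisive.
- **What Mann-Whitney is run on:** week 2 or week 4, raw value or change.

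Two gait variables in the same trial could therefore answer the third objective with different questions, and the data would decide which. Neither branch adjusts the week-4 comparison for baseline as a covariate, although baseline is measured on everyone. With 20 per arm, that precision matters. The gate also suits the Modified Ashworth Scale (MAS) poorly, because it is ordinal.

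**Working it through.** **Inputs from the documents.** Forty participants, 20 per arm (1.1 Summary: 15 + 5 and 11 + 9); 1:1 allocation (1.2 Methods); three visits (1.5 Procedure); significance at 0.05 (SAP), taken as two-sided. There is no sample-size calculation, SD, effect size or correlation, so there is no figure of the plan's own to reproduce.

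**Assumed inputs (none are in the documents).** Log-normal outcome with log-SD 0.5; effect d = 0.6 SD (log scale) at week 4 and half that at week 2; common change 0.15 and 0.3 SD; equal correlation ρ between visits of 0.3, 0.5, 0.7 or 0.8; KS on pooled baseline; Mann-Whitney on week-4 values. "Rising" means that improvement raises the score (walk distance). "Falling" means that it lowers it (Timed Up and Go).

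**Step 1: how often the gate sends such an outcome to the non-normal branch.**

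| KS applied to | Standard KS | Lilliefors |
|---|---|---|
| Pooled baseline | 5-7% | 58-62% |
| Either arm at baseline | about 2% | 56-58% |
| Any arm at any visit | 5-6% | 87-92% |

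For the same outcome the rate runs from about 2% to 92%, depending on choices that the SAP does not make.

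**Step 2: why the interaction costs power, on normal data.** With n = 20 per arm and SD 1, the noncentrality is:

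- Group-by-time, effects (0, d/2, d): (n/2) × (d²/2)/(1−ρ) = 5d²/(1−ρ), on 2 and 76 df.
- ANCOVA at week 4: (n/2) × d²/(1−ρ²) = 10d²/(1−ρ²), on 1 and 37 df.

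The ratio of ANCOVA to interaction is 2/(1+ρ), which exceeds 1 for every ρ below 1, and ANCOVA spends one degree of freedom rather than two. At d = 0.6 and ρ = 0.3: 1.8/0.7 = 2.57 against 3.6/0.91 = 3.96, which gives power of 27% against 49% (simulated: 27.6% and 49.3%).

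If the effect is equal at weeks 2 and 4, or absent at week 2, the interaction's noncentrality rises to 6.67d²/(1−ρ) and the ratio becomes 1.5/(1+ρ), which is below 1 once ρ exceeds 0.5. The advantage then disappears at high correlation. Simulated normal data with equal effects at ρ = 0.7/0.8 gave 72.0/87.1% for the plan with standard KS and 73.2/85.5% for ANCOVA.

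**Step 3: power of the two-stage plan, skewed data** (4,000 trials per cell; no sphericity correction, which would lower ANOVA by 1-3 points).

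| Power (%) at ρ = | 0.3 | 0.5 | 0.7 | 0.8 |
|---|---|---|---|---|
| **Rising:** ANOVA interaction | 29.1 | 37.2 | 58.2 | 73.4 |
| Mann-Whitney, week 4 | 43.6 | 43.3 | 44.7 | 43.6 |
| Two-stage, standard KS | 30.1 | 37.6 | 57.8 | 71.7 |
| Two-stage, Lilliefors | 37.7 | 41.1 | 49.8 | 54.8 |
| ANCOVA | 44.1 | 49.7 | 66.0 | 79.5 |
| Rank-ANCOVA | 46.8 | 52.7 | 67.5 | 80.5 |
| **Falling:** ANOVA interaction | 18.5 | 23.4 | 33.7 | 48.1 |
| Mann-Whitney, week 4 | 44.7 | 42.5 | 42.3 | 44.9 |
| Two-stage, standard KS | 20.5 | 24.9 | 34.4 | 48.2 |
| Two-stage, Lilliefors | 35.4 | 35.9 | 38.8 | 46.7 |
| ANCOVA | 44.4 | 49.3 | 63.8 | 79.6 |
| Rank-ANCOVA | 47.0 | 51.7 | 66.0 | 80.4 |

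The gap between ANCOVA and the plan runs from 44.1 − 37.7 = 6.4 points to 79.6 − 46.7 = 32.9 points. The interaction is weaker than week-4 Mann-Whitney in five of the eight cells. With no effect, rejection rates are 4.2-5.1% (two-stage), 4.4-5.2% (ANCOVA) and 4.4-5.5% (rank-ANCOVA).

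**Step 4: do permitted readings agree?** Varying the KS version and the Mann-Whitney target (week-4 value or change), the readings disagree on p<0.05 in 22-32% of trials for rising scores and 28-37% for falling scores (2,000 trials per cell).

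**Step 5: other open choices, normal data.** Counting either the group main effect or the interaction as success gives about 10% false positives. With a chance baseline difference of 0.5 SD and no effect, week-4 Mann-Whitney rejects in 11-12% of trials, the interaction in 6.5-6.8% and ANCOVA in about 5%.

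**The case against.** The strongest reply is that every listed test is valid, and that the KS gate is not the main cause of the power loss. Read literally, the SAP names the standard KS test. At this sample size that test sends nearly every variable to ANOVA, so outcomes would rarely split between branches. The 92% figure needs the Lilliefors version plus a rule of testing every arm at every visit. The loss under standard KS is almost exactly that of the plain interaction, and in five of eight cells routing to Mann-Whitney would help. The interaction is not blind to baseline, which enters as the first repeated measure.

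All of that is correct and shapes the conclusion: the loss belongs to the two-stage plan as a whole. It does not supply the missing visit, score or deciding contrast.

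The gains are also not uniform. They are about nil for rising scores at ρ = 0.7-0.8 if Lilliefors routes to Mann-Whitney on change (64.9/78.9% against 66.0/79.5%). With no week-2 effect, the standard-KS plan matches ANCOVA for rising scores at 0.5 (50.0% against 49.2%) and leads by 3 to 4 points at 0.7-0.8 (67.2/81.9% against 64.6/77.5%). With equal effects at both visits it is level at 0.7-0.8 (63.9/80.4% against 64.0/79.6%). Falling scores still gain 17 to 22 points over the standard-KS plan under both timings.

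Rank-ANCOVA was simulated on continuous data only, so its power on a coarse, tied scale such as the MAS is untested here.

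**Conclusion.** The concern holds. The specification gap follows from the text alone and needs no assumption: the KS version and target, the deciding ANOVA effect, and the Mann-Whitney visit and score are all unstated, and no one baseline-adjusted MI-versus-HE comparison is fixed.

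The size of the loss does rest on assumptions. With a log-normal outcome, a 0.6 SD effect at week 4 and half of it at week 2, the plan gives up 6 to 25 points of power for rising scores and 9 to 33 for falling scores. With other effect timings the loss can be nil or slightly negative for rising scores. This is a matter of precision and of an open analysis choice; type I error of each single pre-stated test is not at issue. It should be corrected.

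**What to change.** Stop using the KS test to select the analysis. For every continuous outcome, name one MI-versus-HE analysis: ANCOVA of the week-4 value on baseline and group, with residuals inspected. Week 4 is the end of the intervention ("The experimental group received MI with SPCCT and control group received HE with SPCCT intervention 3 times a week for 4 weeks"). Use rank-ANCOVA (ranked week-4 value on ranked baseline and group) as the sensitivity analysis for skewed outcomes. Running it for all continuous outcomes avoids a new data-driven choice. Use it as the main analysis for the ordinal, secondary MAS. Keep the mixed ANOVA time course and the Friedman and Wilcoxon tests as supportive analyses for the within-arm objectives. Section 1.2 randomises within strata that it does not name; if they exist, add them to the model.

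**Cost.** SAP wording and a few lines of code; no new data or visits. Week 2 becomes supportive, and rank-based estimates are harder to interpret. At ρ = 0.3, adjustment adds only about 0 to 3 points over week-4 Mann-Whitney. ANCOVA can be about 6 points below the interaction for rising scores at ρ = 0.8 if the effect appears only at week 4 (77.5% against 83.9%). The Protocol summary already describes forty participants in the past tense, so if outcome data have been seen, the change must be dated and labelled as made after the fact.
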